#### 17.4.2.1.1 Derivation

Patients will be categorised with a censoring indicator variable E:

E =

- 0: no recurrence of original P.aeruginosa until last available follow-up date; or
- 1: *P.aeruginosa* infection has recurred i.e. if and only if genotype of at least one reinfection sample = genotype of baseline infection sample

A time to event (T) in months will be calculated for each patient as  $T = T_1 - T_0$ , where

 $T_0$  = date of randomisation (CRF: *Treatment CRF*, variable: TATRDTD for patients on IV treatment, OCDTCPSD for patients on oral treatment)

If E=0:

 $T_1$  = date of last available follow-up visit (CRF: *Follow-up*, variable: FUVISITD) If F=1.

 $T_1$  = date of first sample taken during follow-up which indicates E=1 (CRF: *Microbiology Form*, variable: MBDSTD.

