#### Table 1: Continuous baseline variables to be reported

Variable	Unit of	Precision	CRF where data are recorded
	measurement	(decimal	
		places)	
BMI z-score	-	2	Derived from height and weight data
(participants			contained in Baseline CRF. See Section
registered at			17.4.2.5.1 below for derivation.
paediatric centres)			
BMI	m/kg²	1	Derived from height and weight data
(participants			contained in Baseline CRF. See Section
registered at centres			17.4.2.5.1 below for derivation.
treating adults)			
Time from	days	0	Baseline – Section 3: date of report
Pseudomonas			confirming P.aeruginosa isolation.
isolation to treatment			Treatment CRFs, Section 1: date started
initiation*			treatment / date started.
%predicted FEV1	litres	2	Raw FEV1 data contained in Baseline
(participants aged 5 or			CRF. See Section 17.4.2.3.1 below for
older only)			derivation.
%predicted FVC	litres	2	Raw FVC data contained in Baseline
(participants aged 5 or			CRF. See Section 17.4.2.3.1 below for
older only)			derivation.
%predicted FVC 25-75	litres	2	Raw FVC data contained in Baseline
(participants aged 5 or			CRF. See Section 17.4.2.3.1 below for
older only)			derivation.
O 2 Saturation	%	2	Baseline

\*Calculated as the number of days from the date of report confirming *P.aeruginosa* isolation to the date of treatment commencement.

Variable	Categories	CRF where data are recorded
Age-group (a)	Infants and toddlers (28 days – 23 mths)	Derived from continuous value obtained from Baseline CRF
	Children (2-11 yrs)	
	Adolescents (12-17 yrs)	
	Adult: 18-64 yrs	
	Elderly adult: ≥ 65 yrs	
Gender	Male	Baseline
	Female	
Pseudomonas	Naïve	Baseline
status	Free	
Other	Candida	Microbiology (see Section
microorganisms	MRSA	17.4.2.12.1 below for derivation)
detected	Burkholderia cepacia	
	Aspergillus	
	Other organisms	
Genotype	F508/F508	Baseline
	F508/other	
	F508/unknown	
	other/other	
	Diagnosis not based on genetics	
Pulmonary	Yes	Baseline (see Section 17.4.2.6.1
Exacerbation	No	below for derivation)

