#### 17.4.2.3.1 Derivation

Three raw spirometry measurements FEV1, FVC, and FEF25-75 are taken at each visit. These are recorded at baseline (CRF: *Baseline*, Variables: BLFEV1R, BLFVCR and BLFEV25I); at follow-up (CRF: *Follow-up*, Variables: FUFEV1R, FUFVCR and FUFEV25I); and at unscheduled visits (CRF: *Unscheduled Visit*, Variables: UVFEV1R, UVFVCR and UVFEV25I).

For the purpose of this analysis, all available lung function measurements will be included.

These are converted to clinically useful measures: %predicted FEV1, %predicted FVC, and %predicted FEF25-75 using a SAS macro available from the global lung initiative [7] which requires as input the participants' raw measurements, their age at the visit (derived from date of visit: FUVISITD or UVVISITD and date-of-birth: FUDOBD or UVDOBD), and their height at the visit (for scheduled visits, this is recorded in FUHGHTR; for unscheduled visits height is not recorded – therefore height should be taken from the closest scheduled visit CRF).

A time variable (days from randomisation) will be derived as Visit Date minus Randomisation Date.

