#### 17.4.2.6.1 Derivation

Pulmonary exacerbations are defined using guidelines by Rosenfeld [4]. They propose a score system for deciding whether the patient is experiencing a pulmonary exacerbation. The score is calculated as follows:

 $PE_{score} = 1.8 \times I_1 + 1.5 \times I_2 + 1.5 \times I_3 + 1.6 \times I_4 + 1.2 \times I_5 + 1.1 \times I_6 - 3.1$  [Eq3]

where  $I_1 = 1$  if decreased exercise tolerance 'present'; 0 otherwise

 $I_2 = 1$  if increased cough 'present'; 0 otherwise

 $I_3 = 1$  if increased sputum/cough congestion 'present'; 0 otherwise

 $I_4 = 1$  if school or work absenteeism 'present'; 0 otherwise

 $I_5$  = 1 if increased adventitial sounds on lung examination 'present'; 0 otherwise

 $I_6 = 1$  if decreased appetite 'present'; 0 otherwise.

If the  $PE_{score} > 2.6$  then the patient is experiencing a pulmonary exacerbation.

If any indicators  $I_1 - I_6$  are coded as missing for whatever reason, they will be assigned the value 0 on the assumption that if the symptom is absent.

Pulmonary exacerbations criteria are captured at baseline and on all follow up visit CRFs along with any unscheduled visit CRFs that may be completed. They relate to the 2 weeks prior to the follow-up visit.

The total number of exacerbations recorded per child during the first 15 months of follow-up is the number of visits for which  $PE_{score} > 2.6$ . Note, we expect that all exacerbations will be measured, as they would usually result in the need for an unscheduled visit.

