#### **19.2 Additional analyses of secondary outcomes**

#### 19.2.1 Sensitivity analysis: Time to reoccurrence of original P.aeruginosa infection

Derivation as in Section 17.4.2.1.1 but  $T_0$  amended to be date of treatment commencement rather than date of randomisation. Analysis as in Section 17.4.2.1.2.

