#### **19.2.2** Time to first pulmonary exacerbation

#### 19.2.2.1 Derivation

Derivation of pulmonary exacerbation as outlined in Section 17.4.2.6.1. Patients will be categorised with a censoring indicator variable E:

E = 0: no visits for which  $PE_{score} > 2.6$ ; or

1: there was at least one visit during follow-up for which  $PE_{score} > 2.6$ .

A time to event (T) in months will be calculated for each patient as  $T = T_1 - T_0$ , where

T0 = date of first treatment (CRF: *Treatment CRF*, variable: TATRDTD for patients on IV treatment, OCDTCPSD for patients on oral treatment)

If E=0:

T1 = date of last available follow-up (CRF: *Follow-up*, variable: FUVISITD)

If E=1:

 $T_1$  = first visit date which indicates E=1 (CRF: *Follow-up*, variable: FUVISITD).

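### SAP 17.4.2.1.1 labels T0 as randomisation but names the treatment-start fields, and 19.2.2.1 dates first exacerbations from the scheduled-visit field only

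*SAP*

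**What the plan says.** **Origin for time to recurrence.** SAP 17.4.2.1.1 defines T0 as "date of randomisation (CRF: *Treatment CRF*, variable: TATRDTD for patients on IV treatment, OCDTCPSD for patients on oral treatment". SAP 19.2.2.1, for time to first pulmonary exacerbation, defines T0 as "date of first treatment (CRF: *Treatment CRF*, variable: TATRDTD for patients on IV treatment, OCDTCPSD for patients on oral treatment". The CRF and both variables are the same; only the label differs. SAP 19.2.1 plans a sensitivity analysis of the recurrence outcome in which T0 is "amended to be date of treatment commencement rather than date of randomisation". Everything else is carried over, and no field is named.

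**What the Treatment CRF date is.** For the interval from isolation to treatment initiation, Table 1 gives the source of the treatment date as "Treatment CRFs, Section 1: date started". For lung function, 17.4.2.3.1 uses a separate randomisation date: "A time variable (days from randomisation) will be derived as Visit Date minus Randomisation Date".

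**Dates for first exacerbation.** In 19.2.2.1 the event date is the "first visit date which indicates E=1 (CRF: *Follow-up*, variable: FUVISITD", and the censoring date is the "date of last available follow-up (CRF: *Follow-up*, variable: FUVISITD". The exacerbation definition is imported from 17.4.2.6.1. That section collects the criteria on unscheduled-visit CRFs as well as follow-up CRFs, and it expects all exacerbations to be measured, "as they would usually result in the need for an unscheduled visit".

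**The concern.** One pair of fields cannot hold both the randomisation date and the date of first treatment. If the fields are treatment-start dates, the recurrence analysis described as running from randomisation does not do so when built from the named variables. The sensitivity analysis meant to test the choice of origin would then have nothing to test, and its agreement with the main result could be reported as robustness when the two are the same calculation.

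The second fault is independent of the first. In 19.2.2.1 T0 agrees with its label; the problem lies in T1. The event indicator draws on scheduled and unscheduled visits, while the event date draws on the scheduled-visit field only. The SAP expects exacerbations usually to lead to an unscheduled visit, so the visits without a usable date are the ones where most first events should be found.

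**Working it through.** The plan gives no figure to reproduce on this point, so the check is a comparison of the field definitions.

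**Step 1: what TATRDTD and OCDTCPSD record.** Three features of the SAP indicate treatment start:
- Table 1 describes the date on the Treatment CRFs as the date treatment started.
- The fields are arm-specific, one for IV and one for oral. A randomisation date would not need a different variable in each arm.
- SAP 17.4.2.3.1 treats the randomisation date as an item in its own right.

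**Step 2: consequence for 19.2.1.** Let R be the randomisation date and S the treatment-start date.

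| How the main analysis is programmed | Main T | Sensitivity T | Main minus sensitivity |
|---|---|---|---|
| From the named fields | T1 − S | T1 − S | 0 for every patient |
| From the label | T1 − R | T1 − S | S − R |

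In the first row T and E are unchanged for every patient, so the Kaplan-Meier curves, the log-rank test and any Cox model are identical. In the second row the sensitivity analysis does its job.

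**Step 3: size of S − R.** The SAP does not give it. The nearest figure is the ineligibility category in 14.1 for patients unable to start treatment within 21 days of the positive microbiology report. That interval runs from the report, not from randomisation. It bounds S − R only on two assumptions: that randomisation falls on or after the report, and that the limit is kept. On those assumptions S − R is 0 to 21 days, or 0 to 21/28 = 0.75 of the 28-day month defined in 8.9.

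**Step 4: T1 for first exacerbation.** SAP 17.4.2.3.1 lists the Follow-up and Unscheduled Visit CRFs separately, with visit dates FUVISITD and UVVISITD. Using FUVISITD alone gives these results:

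| Patient | E | T1 from FUVISITD alone |
|---|---|---|
| First qualifying visit is scheduled | 1 | Correct |
| First qualifying visit is unscheduled; a later scheduled visit also scores above 2.6 | 1 | Too late |
| First qualifying visit is unscheduled; no scheduled visit scores above 2.6 | 1 | None defined |
| No qualifying visit; last contact was unscheduled | 0 | Censored too early |

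**Step 5: can the delay be bounded?** Scheduled visits are planned every 12 weeks (12 × 7 = 84 days), but 84 days is not a bound. A later scheduled visit supplies T1 only if it also scores above 2.6, and the criteria cover just the two weeks before a visit. SAP 8.9 also reports many visits outside their windows.

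**Step 6: the same field elsewhere.** In 17.4.2.1.1 the event date is the microbiology sample date and is not affected. The censoring date is FUVISITD only, so a patient last seen at an unscheduled visit is censored early there too.

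**The case against.** The strongest reply is that the intent is clear in words. SAP 17.4.2.1.1 says randomisation, and 19.2.1 contrasts treatment commencement with it. A programmer who follows the label and finds the true date will run two different analyses, and 5 (Statement of Compliance) provides for testing and validation of the programs. This stands in part: redundancy follows only if the named fields are used. It does not remove the contradiction. Programs are built from named variables, no randomisation-date variable is named, and validation against this text could pass either version.

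A second reply is that follow-up CRF may cover both visit types, as in 17.4.2.7.1. That section still assigns FU-prefixed variables to scheduled visits and UV-prefixed variables to unscheduled ones, and 19.2.2.1 names only FUVISITD.

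A reader might also infer more than the SAP supports:
- **That an arm difference in waiting time would be hidden.** Table 1 reports time from the positive report to treatment start, and 17.2 splits baseline tables by arm. That interval contains any wait after randomisation, provided randomisation follows the report.
- **That exacerbations at unscheduled visits would be dropped.** By the imported definition they still set E=1. What is missing or wrong is the date.
- **That the errors are capped at 21 days and 12 weeks.** The first figure needs the two assumptions above, and the second is not a bound.

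**Conclusion.** The point holds as two errors in variable mapping. First, the label and the fields for T0 in 17.4.2.1.1 conflict. If the fields are followed, 19.2.1 repeats the main recurrence analysis exactly. It would go too far to say that the from-randomisation analysis will certainly never be run, because the SAP does not settle whether label or field prevails. Second, 19.2.2.1 leaves T1 undefined or late for a patient whose first qualifying visit is unscheduled, and can censor others early.

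The reach is limited to one secondary outcome, its sensitivity analysis and one additional analysis. The primary outcome is untouched. The gap from randomisation to treatment is not given, the delay in event dating cannot be bounded from the SAP, and no effect on a log-rank result or direction of bias can be shown. The correction is still worth making before programming, because the rules as written give a wrong or undefined result and the repair is nearly free.

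**What to change.** - **17.4.2.1.1, T0:** take it from the randomisation record and name that variable. SAP 17.4.2.3.1 uses the randomisation date but gives no variable name, so a cross-reference is not enough.
- **19.2.1 and 19.2.2.1, T0:** keep TATRDTD and OCDTCPSD, and state them explicitly in 19.2.1.
- **19.2.2.1, T1 when E=1:** the earliest FUVISITD or UVVISITD at which the exacerbation score exceeds 2.6.
- **19.2.2.1, T1 when E=0:** the latest FUVISITD or UVVISITD.
- **17.4.2.1.1, T1 when E=0:** review the FUVISITD-only censoring date in the same way.

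The cost is a few words in the SAP and the variable names in the two time-to-event programs. No new data are needed: both visit dates are already named in 17.4.2.3.1, which also already relies on the randomisation date.

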#### 8.9 Schedule of assessments

Table 3 in Section 7 of the protocol outlines the schedule of assessments.

Note that for the purpose of this trial, a 'month' is defined as 28 days. Visits should have occurred as follows:

	Scheduled study visit	Time after treatment start
T 3	3 months	12 weeks
$T_6$	6 months	24 weeks
T 9	9 months	36 weeks
T 12	12 months	48 weeks
T 15	15 months	60 weeks
T 18	18 months	72 weeks
T 21	21 months	84 weeks
T 24	24 months	96 weeks

Due to large numbers of visits occurring outside of appropriate visit windows and not consistently being captured on scheduled or unscheduled visit CRFs; where outcomes refer to specific time points, data will be included based on dates of assessments rather than CRF names. For an assessment to be associated with a particular time-point it must have occurred within 1 week either side of the expected visit date, apart from  $T_{15}$  which may be minus 1 week or plus 2 weeks of the expected visit date.

Not all patients were followed up after  $T_{15}$ .  $T_{18}$ ,  $T_{21}$  and  $T_{24}$  were proposed in the protocol up to and including version 7. Patients randomised after 1st January 2016 were required to complete up to and including  $T_{15}$  only.

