#### 17.4.2 Secondary outcomes

#### 17.4.2.1 Time to reoccurrence of original *P.aeruginosa* infection

Only patients who have a baseline sample and at least one sample post three months will be included in this analysis.

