#### 17.4.2.1.2 Analysis

The outcome T will be presented graphically using Kaplan-Meier curves, stratified by treatment group. E=0 denotes a censored observation. Difference between the two treatment arms will be tested using the log-rank test. If there is imbalance in the randomisation, Cox proportional hazards regression may be used to calculate a hazard ratio with 95% CI, comparing the IV treatment group to oral, whilst adjusting for baseline variables for which there is imbalance. From inspection of the Kaplan-Meier plot the separation between the curves should remain proportional across analysis time. If the curves cross again this shows that the proportional hazards assumption has been violated. To put this formally, the proportional hazards assumption is that the ratio of hazards is a constant that does not depend on time:

$$\frac{h_A(t)}{h_B(t)} = r$$
 [Eq1]

When this assumption fails, it is because the hazard ratio changes over time. To test this, we will add predictor for (treatment arm)\*time interaction i.e. a time-dependent covariate. Evidence that (treatment arm)\*time interaction is not zero is evidence against proportional hazards. In SAS, PROC PHREG provides the p-value of this test. p<0.05 will indicate non-proportional hazards and thus a time-dependent covariate will be included in the Cox model. If p<0.05 it may not be possible to present result from which conclusions may be drawn.

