#### 19.1.3 Results of blind review

Derivation and analysis as in Section 17.4.1.1 and Section 17.4.1.2 but all patients that have been followed up for more than 15 months but not had a sample within the 15 month window will be included. These patients will be classified as success or failure based on the next sample that was taken following the 15 month window.

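### Recurrence is dated by culture but event-free patients are censored at their last visit, so any follow-up after the last culture counts as recurrence-free time at risk

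*SAP*

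**What the plan says.** Section 17.4.2.1.1 makes recurrence an event "if and only if genotype of at least one reinfection sample = genotype of baseline infection sample". The two end dates come from different forms:

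- For E=1, T1 is the "date of first sample taken during follow-up which indicates E=1 (CRF: *Microbiology Form*, variable: MBDSTD").
- For E=0, T1 is the "date of last available follow-up visit (CRF: *Follow-up*, variable: FUVISITD").

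Section 17.4.2.1 sets the entry rule: "Only patients who have a baseline sample and at least one sample post three months will be included in this analysis". In section 17.4.2.1.2, "E=0 denotes a censored observation" in the Kaplan-Meier analysis, and "Difference between the two treatment arms will be tested using the log-rank test".

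Two variations are planned. After blind review, section 17.4.2.1.2 assigns patients without both samples sent for genotyping first to E=0 and then to E=1. Section 19.2.1 changes the time origin T0. Neither changes the censoring date.

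**The concern.** When an event can be found only by an assessment, a patient is known to be event-free only up to the last assessment able to show it. Here that is the last culture. A visit without a sample says nothing about recurrence, yet under this rule it extends the recurrence-free time. The entry rule does not prevent this, because one sample after three months is enough and none is needed near the censoring date. The primary outcome is better protected: section 17.4.1.1 leaves out a patient without regrowth who has no sample in the 15-month window.

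There is also a mismatch in the other direction. FUVISITD is the Follow-up form date; section 17.4.2.3.1 gives unscheduled visits their own variable, UVVISITD. Section 17.4.1.1 says that the Microbiology form covers samples from scheduled and unscheduled visits. Read literally, a positive culture at an unscheduled visit after the last Follow-up form is an event on its own date, while a negative culture on that day adds no time at risk.

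At stake are the recurrence curves for the first secondary outcome listed in section 9.2 and, if sampling differs by arm, its log-rank test and any hazard ratio.

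**Working it through.** The SAP gives no event rate, sample size or sampling frequency for this outcome, so it has no figure to reproduce. The mismatch follows from the text. Its possible size can only be illustrated.

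**Inputs.** From section 8.9: visits every 12 weeks, with 3 months = week 12 and 15 months = week 60. Assumed: constant recurrence hazard from week 12, true recurrence 20% by week 60, detection at the next culture, everyone attends to week 60, and a share q of patients has no culture at the last r visits for reasons unrelated to recurrence.

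**Recurrence detectable in a patient without the last r cultures.** Cultures then stop 4 − r intervals after week 12, so p(r) = 1 − 0.8^((4 − r)/4).

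- p(1) = 1 − 0.8^0.75 = 15.4%
- p(2) = 1 − 0.8^0.5 = 10.6%
- p(3) = 1 − 0.8^0.25 = 5.4%

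**Last-visit censoring.** Nobody leaves the risk set before week 60 without an event, so the Kaplan-Meier estimate is the crude proportion (1 − q) × 20% + q × p(r).

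| q | r | Estimate | Relative shortfall against 20% |
|---|---|---|---|
| 0 | any | 20.0% | 0% |
| 10% | 1 | 0.9 × 20 + 0.1 × 15.4 = 19.5% | 2% |
| 20% | 2 | 0.8 × 20 + 0.2 × 10.6 = 18.1% | 9% |
| 30% | 2 | 0.7 × 20 + 0.3 × 10.6 = 17.2% | 14% |
| 30% | 3 | 0.7 × 20 + 0.3 × 5.4 = 15.6% | 22% |

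**Last-culture censoring.** Unsampled patients leave the risk set after their last culture. The detected probability in each interval stays at 1 − 0.8^0.25 = 5.4% among those still sampled, and 1 − (0.8^0.25)^4 = 20%. The shortfall disappears under these assumptions.

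**Second illustration.** In a simulation with 30% true recurrence, 10%, 20% or 30% of patients stop giving cultures at a random visit but attend to month 15. Last-visit censoring gives 28.4%, 26.6% and 24.6%; last-culture censoring gives 30.3%, 30.1% and 30.0%. With no gaps the two rules agree.

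**Between arms.** With equal gaps and equal true recurrence, both arms shift together. With no treatment effect but q = 10% in one arm and 30% in the other (r = 2), the estimates are 0.9 × 20 + 0.1 × 10.6 = 19.1% and 17.2%, a ratio of 0.90. For the test, assume 200 to 400 patients in total (not an SAP figure), so about 36 to 72 events at the mean rate of 18.1%. The shift in the log-rank Z is roughly |ln 0.90| × √events / 2 = 0.31 to 0.44. The two-sided type I error is then about 6.1% to 7.3% instead of 5%.

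**The case against.** The strongest reply is that the SAP does not document the pattern that does harm, which is attended visits after the last culture. A reader might infer it from two places, but neither supports it. Section 19.1.3 says "all patients that have been followed up for more than 15 months but not had a sample within the 15 month window will be included", but classifies those patients on their next sample, so they do have a later culture. Their gap lies in the interior of follow-up, and last-culture censoring would treat it in the same way. Section 8.9 describes visits "not consistently being captured on scheduled or unscheduled visit CRFs"; that concerns which form a visit was recorded on, not absent samples. A missing sample in the 15-month window can also come from an off-window visit or a withdrawal. This stands: the frequency of terminal gaps is unknown and may be zero.

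A reader might also infer that the comparison favours one arm. The documents do not support that. The visit schedule is common to both arms, and an open-label design alone does not show unequal sampling.

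Three further points stand in part. The E=0 and E=1 analyses after blind review bound uncertain event status for patients without genotyped samples, but leave T1 alone and need not cover every affected patient. FUVISITD may be shorthand for any visit: section 19.2.2.1 also names only that variable for the first exacerbation visit, although section 17.4.2.6.1 counts unscheduled visits. Taken literally, its loss of time at risk works against the main bias. Finally, if patients stop giving samples because they are well, last-culture censoring is itself informative and biases recurrence upwards.

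None of this makes the stated rule right. It limits what can be said about its effect.

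**Conclusion.** The point holds as a defect in the derivation: event and censoring dates come from different sources, and culture-free time at the end of follow-up is treated as observed freedom from recurrence. The resulting bias in the Kaplan-Meier estimate is towards too little recurrence. Its size cannot be read from the SAP. It is nil if every last visit yields a culture; in the central illustration it is about 2 percentage points (20% to about 18%). That figure rests on assumed recurrence, an assumed share of unsampled patients, and sampling that stops for reasons unrelated to recurrence. Bias between arms is conditional on gaps that differ by arm; even the assumed 10% against 30% case moves the test only modestly. This is an alignment error in one secondary outcome, worth correcting because the correction is cheap. It is not evidence that the comparison is biased, and it does not touch the primary analysis.

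**What to change.** In section 17.4.2.1.1, define T1 for E=0 as the date of the patient's last respiratory sample cultured, whatever its result, from any scheduled or unscheduled visit (last MBDSTD on the Microbiology form). The words on result matter, because a last P. aeruginosa culture could be read as the last positive one. The same line removes the mismatch for unscheduled visits. Section 19.2.1 takes its derivation from 17.4.2.1.1 and needs no separate edit. Last-visit censoring can be kept as a sensitivity analysis if wanted.

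The cost is one line of text, using a date already collected. The downside is slightly less nominal follow-up and reliance on stopping sampling being unrelated to recurrence.
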